6.5 Participant Withdrawal/Discontinuation Criteria

Participants may discontinue study treatment at any time for any reason or be dropped from the study treatment at the discretion of the treating investigator should any untoward effect occur. In addition, a participant may be discontinued from study treatment by the treating investigator or the P.I. if study treatment is inappropriate, the trial plan is violated, or for administrative and/or other safety reasons. Specific details regarding procedures to be performed at study treatment discontinuation are provided in [Section 8.1.4 – Other Procedures](#).

A participant must be discontinued from study treatment but continue to be monitored in the study for any of the following reasons:

- The participant or participant's legally acceptable representative requests to discontinue study treatment
- Confirmed radiographic disease progression outlined in [Section 8.1.2.5.1](#)
- Any progression or recurrence of any malignancy, or any occurrence of another malignancy that requires active treatment
- Unacceptable adverse experiences as described in [Section 6.2.2](#).
- The participant has a medical condition or personal circumstance which, in the opinion of the treating investigator and/or P.I., placed the participant at unnecessary risk from continued administration of study treatment.
- The participant has a confirmed positive serum pregnancy test
- Noncompliance with study treatment or procedure requirements
- Recurrent Grade 2 pneumonitis
- The participant is lost to follow-up
- Administrative reasons

6.6 Participant Replacement Strategy

Patients that are not treated by intention to treat will be replaced to the total 33 patients intended. All patients who receive the first dose of pembrolizumab will be included in analysis per intention to treat. Patients who receive at least one dose of pembrolizumab and then do not proceed to surgery will be considered grade 3 response.

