2.2 Trial Diagram

3.0 OBJECTIVES & HYPOTHESES

3.1 Primary Objective & Hypothesis

Objective:

To determine the pathologic complete response (pCR) rate in patients with cT1b-T2N0 GEA treated with neoadjuvant pembrolizumab followed by surgical resection.

Regression of the primary tumor will be documented by the amount of viable tumor versus the amount of fibrosis (Becker Criteria), ranging from no evidence of any treatment effect to a complete response with no viable tumor identified, as previously described[1] [Grade 1a: complete remission (pCR), no residual tumor/tumor bed; Grade 1b: subtotal remission, <10% residual tumor/tumor bed; Grade 2: partial remission, 10-50% residual tumor/tumor bed; Grade 3: minor/no remission, >50% residual tumor/tumor bed].

Hypothesis:

The pCR rate (Grade 1a+b response) in patients with cT1b-T2N0 GEA who receive neoadjuvant pembrolizumab followed by surgical resection will be 15%, whereas historical patients treated with surgery alone have a pCR rate of virtually 0%. [2, 3]

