3.2 Secondary Objectives & Hypotheses

Objectives:

- To determine the R0 resection rate in patients with cT1b-2N0 GEA treated with neoadjuvant pembrolizumab. Proximal, distal, and circumferential margins will be assessed to determine the completeness of resection. The absence of tumor cells at the proximal and distal margins will be required to be classified as an R0 resection.
- To determine rates of Grade 1a (complete); 1b (minimal residual disease); 2 (partial response); and 3 (no response) pathologic response grades (PRG).
- To evaluate the safety/ tolerability of pembrolizumab in patients with cT1b-2N0 GEA
- To determine the DFS measured from the time of first pembrolizumab dose
- To determine OS measured from the time of first pembrolizumab dose

Hypotheses:

- a. R0 resection rate will be greater than 95%.
- b. A subset of cases will be G1b and G2 responses.
- c. Pembrolizumab will be safe and tolerable. Patients will successfully complete neoadjuvant therapy and undergo surgery 8-11 weeks after first dose of pembrolizumab.
- d. The DFS rate will be improved compared to historical controls.
- e. OS will be improved compared to historical controls.

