3.3 Exploratory Objectives

- a. To evaluate rates of PD-L1 positive expression (by CPS score ≥ 1 and ≥ 10), MSI status, TMB and EBV status in pre-treatment biopsy specimens.
- b. To evaluate whether PD-L1 expression, MSI status, TMB and/or EBV status in pre-treatment biopsy specimen is a predictive biomarker for pCR/PRG/R0 to pembrolizumab and other clinical outcomes.
- c. To evaluate interval change in PD-L1 expression (by CPS score) pre/post pembrolizumab therapy in resected pathological specimens (if residual tumor is present).
- d. To determine the somatic genomic changes of actionable cancer related genes (mutation, amplification, indels, and translocation) using targeted deep next-generation sequencing (NGS) oncopanel in pre-treatment specimen and in resected specimen (if tumor is still present) and correlate with clinical outcomes (pCR/PRG, R0 rate, DFS, OS) and other molecular markers.
- e. To evaluate ctDNA NGS pre-pembrolizumab, post-pembrolizumab, post-surgery, and if applicable at time of recurrence, and correlate with clinical outcomes (pCR/PRG, R0 rate, DFS, OS) and molecular markers.
- f. To determine baseline and interval changes in whole-exome RNAseq expression analysis pre-/post- therapy.
- g. To evaluate fecal flora via Fecal 16S RNA seq pre-pembrolizumab, post-pembrolizumab, post-surgery, and if applicable at time of recurrence, and correlate with clinical outcomes.

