9.0 STATISTICAL ANALYSIS PLAN

9.1 Statistical Analysis Plan Summary

9.2 Statistical Analysis Plan

At our institution, patients with cT1b-2N0M0 GEA typically undergo surgery alone without additional therapy. Thus, we expect 100% of resected specimens to have evidence of cancer in historical controls. We hypothesize that neoadjuvant pembrolizumab will result in a pCR rate (Grade 1a+1b) of 15%. A sample size of 33 patients will provide 90% power with one-sided alpha 0.1 to detect this pCR rate using neoadjuvant pembrolizumab. More specifically, we will use an optimal, Simon two-stage design to test the null hypothesis that the Grade 1 response rate is 1% vs. the alternative that it is 15%. Fifteen patients will be enrolled in the first stage and if no complete pathological responses are observed the trial will be terminated for futility. If one or more responses are seen, an additional 18 patients will be studied for a total of 33. Two or more responses in 33 patients will indicate that the treatment is promising, whereas 0/15 or 1/33 will be considered a negative result. Patients who receive pembrolizumab but do not go to surgery will be counted as not having achieved a pCR.

We will also assess activity in the subset of patients who are PD-L1 positive. Assuming an approximate PD-L1 positivity incidence (CPS score ≥ 1) of 50% of all patients enrolled, this sample size of 16 expected PD-L1 positive patients will provide over 95% power with one-sided alpha 0.05 to detect a pCR rate (Grade 1a+1b) of 30% vs. 1% using neoadjuvant pembrolizumab in this preplanned subset. Using a higher CPS cutoff of ≥ 10 we assume 20% of patients will be PD-L1 positive based on recent data, and the sample size of 7 expected PD-

L1 positive patients will provide 67% power with one-sided alpha 0.05 to detect a pCR rate (Grade 1a+1b) of 30% vs. 1%

Complete responses (R0) will be tabulated along with an exact 90% confidence interval. DFS and OS will be estimated using the Kaplan-Meier method. Adverse events will be summarized by type, grade, and attribution to the study drug.

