Chi-square tests and Spearman or Pearson correlation coefficients will be calculated to assess associations among the correlative endpoints. Comparisons of pre-treatment PD-L1 expression and other markers between responders and non-responders will be performed using two-sample t or Wilcoxon rank-sum tests. Changes in tumor markers will be analyzed using paired t or Wilcoxon signed rank tests. If the number of events is sufficient, Cox regression models will be fit to determine whether tumor markers are predictive of DFS and OS.

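### Section 6.6 gives unresected patients a histologic Grade 3 without a specimen, so the secondary Grade 3 rate mixes non-resection with observed lack of pathologic response

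*Combined protocol and SAP*

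**What the plan says.** Section 6.6 sets the analysis population: "All patients who receive the first dose of pembrolizumab will be included in analysis per intention to treat". It then fixes what happens to those who are dosed but not operated on: "Patients who receive at least one dose of pembrolizumab and then do not proceed to surgery will be considered grade 3 response".

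Section 3.1 takes its grades from the Becker criteria, which compare viable tumor with fibrosis. The lowest category is "Grade 3: minor/no remission, >50% residual tumor/tumor bed".

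Section 3.2 makes the grade distribution a secondary objective: "To determine rates of Grade 1a (complete); 1b (minimal residual disease); 2 (partial response); and 3 (no response) pathologic response grades (PRG". Section 3.3 asks whether each of several pre-treatment markers "is a predictive biomarker for pCR/PRG/R0 to pembrolizumab and other clinical outcomes", and relates genomic and ctDNA findings to the same grades.

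For the primary endpoint, section 9.2 handles the same patients without using a grade: "Patients who receive pembrolizumab but do not go to surgery will be counted as not having achieved a pCR". Its one named marker-by-response test is binary: "Comparisons of pre-treatment PD-L1 expression and other markers between responders and non-responders will be performed using two-sample t or Wilcoxon rank-sum tests". Section 9.2 gives no method for the grade rates. No section provides a separate category for unresected patients, a grade table limited to resected patients, or a statement on whether assigned grades enter the grade-marker analyses.

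**The concern.** A grade defined by residual tumor in the tumor bed is a measurement on a specimen. Section 6.6 enters a value for patients who have none. For a yes/no endpoint, counting them as failures is a sound convention. For a distribution across four histologic categories, it fills one category with something else.

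Patients may miss surgery for reasons that say little about tumor regression. Section 6.5 lists reasons for stopping study treatment that include participant request, adverse experiences, pregnancy, noncompliance, loss to follow-up and administrative reasons, as well as progression. Some of these patients may also not reach surgery, and section 6.6 treats all causes alike. Two things are at stake: how the secondary Grade 3 rate is read, and the meaning of any ordinal association between grade and a marker.

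**Working it through.** **1. The primary design does not depend on the label.** Section 9.2 gives 15 patients in stage 1, stopping at 0 responses; 33 in total; success at 2 or more; rates of 1% against 15%; 90% power; one-sided alpha 0.10. Success fails only if stage 1 has no response, or if stage 1 has exactly one and the next 18 have none. So

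P(success) = 1 − (1−p)^15 − 15·p·(1−p)^32.

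- p = 0.15: 1 − 0.0874 − 0.0124 = 0.900. The stated 90% is reproduced.
- p = 0.01: 1 − 0.8601 − 0.1087 = 0.031, within the 0.10 limit.

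Only response or non-response enters. An unresected patient is a non-response under 9.2 whether called Grade 3 or ungraded.

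**2. Effect on the Grade 3 rate.** Let x be the number of observed Grade 3 specimens and k the number dosed but unresected, with 33 treated. Neither x nor k is given in the documents. I assume x = 10, 15 or 20 and k = 1, 3 or 5.

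- Rate under 6.6: (x + k)/33.
- Observed Grade 3 over all treated: x/33. The rule adds k/33.
- Rate among resected patients: x/(33 − k).
- Excess over the resected-only rate: (x + k)/33 − x/(33 − k) = (k/33)·[1 − x/(33 − k)].

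Example, x = 15 and k = 3: 18/33 − 15/30 = 54.5% − 50.0% = 4.5 points.

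| k | k/33 (points) | Excess, x = 10 | Excess, x = 15 | Excess, x = 20 |
|---|---|---|---|---|
| 1 | 3.0 | 2.1 | 1.6 | 1.1 |
| 3 | 9.1 | 6.1 | 4.5 | 3.0 |
| 5 | 15.2 | 9.7 | 7.0 | 4.3 |

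With k = 0 every entry is zero. For scale, the exact 90% interval in the example is 38.9% to 69.5% under the rule and 33.9% to 66.1% among resected patients.

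**3. Effect on an ordinal grade-marker correlation.** This is an illustrative simulation with 33 patients, an assumed latent correlation of 0.5, assumed grades of 15% Grade 1, 35% Grade 2 and 50% Grade 3, and non-resection unrelated to the marker. The mean Spearman magnitude with all true grades known is about 0.42 to 0.43. With imputed grades it is 0.41 at k = 1, 0.39 at k = 3 and 0.36 at k = 5. Restricted to resected patients it stays at 0.42 to 0.43.

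**4. The named binary marker test.** With 0.15 × 33, about 5, expected responders there are 28 non-responders. Three unresected patients would be 3/28 = 11% of them. They are in that group because 9.2 counts them as having no pCR, so the Grade 3 label does not change the figure.

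**The case against.** The strongest reply is that the rule is explicit, pre-specified, conservative for the primary endpoint and consistent with section 9.2. Section 3.2 itself glosses Grade 3 as no response. Read as a composite of Grade 3 or not resected among all treated patients, the rate is legitimate if labelled so. The grade hypothesis in 3.2 concerns only Grades 1b and 2, and no test uses the Grade 3 rate. Hypothesis c in 3.2 makes reaching surgery an outcome, so the number unresected should be visible anyway. Sections 6.2.2 and 8.1.1.8 send patients whose dosing delay threatens the surgical window straight to surgery, so some of them can still yield a specimen.

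All of this stands, and it rules out several stronger readings that a reader might infer:

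- *The Grade 3 rate is wrong, or necessarily overstated.* The true grades of unresected patients are unknown, and some may miss surgery because of progression. What the documents show is a mixture under a histologic name.
- *The bias is the full 3.0 points per patient.* That takes every unresected patient as certainly not Grade 3. The resected-only comparison gives less.
- *The rule distorts the responder versus non-responder marker test.* The 11% above follows from 9.2, whatever the label.
- *Unresected patients should be dropped from the marker analyses.* That conditions on a post-treatment event and departs from the intention-to-treat rule in 6.6. It belongs in a sensitivity analysis.

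What the reply does not answer is that nothing in the plan calls for the composite label, the separate row or the resected-only table.

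**Conclusion.** The point holds as a minor one about a secondary endpoint. Followed as written, the plan reports under a category defined by residual tumor a rate that includes patients with no tumor specimen. Any ordinal grade-marker analysis that uses the assigned grade inherits the same mixture; the documents do not say whether it will.

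Against the resected-only rate the size is about 1 to 2 points for one unresected patient, 3 to 6 for three and 4 to 10 for five. This rests on assumed attrition and on 10 to 20 observed Grade 3 specimens among 33 treated. The resected-only rate is itself only a benchmark, since it describes patients who reached surgery. The weakening of an ordinal correlation is modest and depends on the simulation's assumptions. The primary test, its power and alpha, and the counts of Grades 1a, 1b and 2 do not change.

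**What to change.** - In section 6.6, replace the Grade 3 assignment with a statement that patients who receive at least one dose and do not undergo resection are counted as not having achieved a pCR (non-responders) in the primary analysis, consistent with section 9.2.
- In the pathologic response table, keep all treated patients as the denominator, show only observed grades in the four grade rows, and add a 'not resected' row. Beside it, give the grade distribution among resected patients.
- For ordinal grade-marker analyses, add a sensitivity analysis restricted to observed grades, labelled as conditional on reaching surgery. In any version that includes unresected patients, state how they are coded.

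The cost is one reworded sentence, one table row, one extra column and one sensitivity analysis. Sample size, decision rule and data collection stay as they are.

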6.7 Clinical Criteria for Early Trial Termination

Early trial termination will be the result of the criteria specified below:

1. Quality or quantity of data recording is inaccurate or incomplete with $\geq 10\%$ of data unavailable.
2. Poor adherence to protocol and regulatory requirements
3. Incidence or severity of adverse drug reaction in this or other studies indicates a potential health hazard to participants
4. Plans to modify or discontinue the development of the study drug
5. If patient deaths or excessive toxicity attributed to the investigational drug are seen in the 30 days following surgery. A **30-day post-operative** death rate of $\geq 5\%$ attributed to study agent is considered unacceptable. The relationship of the investigational drug to the mortality will be determined by the treating medical oncologist and surgeon.

In the event of Merck decision to no longer supply study drug, ample notification will be provided so that appropriate adjustments to participant treatment can be made.

7.0 TRIAL FLOW CHART

7.1 Study Flow Chart

Pre-treatment research biopsy for pathologist review	X								
Pre-treatment biopsy for biomarker analysis ^c	X								
Resected surgical specimen for pathologist review						X			
Resected surgical specimen for biomarker analysis ^{c,d}						X			
Foundation One CDx	X					X ^d			
Guardant 360 ctDNA collection and blood banking ^l	X				X		X		X ^k
Stool collection	X				X		X		X ^k

^aCT scan of chest/abdomen/pelvis with IV and PO contrast, OR MRI of abdomen/pelvis plus non-contrast chest CT if contraindication to iodinated dye.

^bOnly needed in women of childbearing potential

^cBiomarker analysis includes testing for MSI via immunohistochemistry (IHC), HER2 testing (via IHC and/or fluorescence in situ hybridization (FISH)), Epstein-Barr encoding region in situ hybridization (EBER ISH), PD-L1 CPS testing, and whole-exome RNAseq expression

^dWill only be able to be performed if there is residual tumor left in surgical specimen

^eSurveillance visits with physician (or nurse practitioner or physician assistant) will occur every 3 months until year 3 post surgery, and then every 6 months until year 5 post surgery

^fSurveillance imaging will be performed annually for 2 years post-surgery and then as clinically indicated

^gWill only be performed as needed

^hWill be checked every 3 months until year 3 post surgery, and then every 6 months until year 5 post surgery

ⁱTSH only be checked, and FT4 and T3 only checked reflexively if TSH is abnormal, per routine care.

^jPatients will come off study 5 years post-surgery, if cancer recurs, or if patient withdraws consent. However, overall survival follow-up will continue to year 5 if cancer recurs or if patient withdraws consent from treatment but not follow up.

^kWill only be collected if patient's gastroesophageal cancer recurs

^lBlood Banking collected and processed per IRB16294A (see [Section 8.1.2.6](#) of this protocol).

^mEndoscopy must be conducted at enrolling institution (see [Section 8.1.2.6.2](#) of this protocol).

8.0 TRIAL PROCEDURES

8.1 Trial Procedures

The Trial Flow Chart - [Section 7.0](#) summarizes the trial procedures to be performed at each visit. Individual trial procedures are described in detail below. It may be necessary to perform these procedures at unscheduled time points if deemed clinically necessary by the investigator.

Furthermore, additional evaluations/testing may be deemed necessary by the P.I. and/or Merck for reasons related to participant safety. In some cases, such evaluation/testing may be potentially sensitive in nature (e.g., HIV, Hepatitis C, etc.), and thus local regulations may require that additional informed consent be obtained from the participant. In these cases, such evaluations/testing will be performed in accordance with those regulations.

8.1.1 Administrative Procedures

8.1.1.1 Informed Consent

The Investigator must obtain documented consent from each potential participant prior to participating in a clinical trial.

8.1.1.1.1 General Informed Consent

Consent must be documented by the participant's dated signature or by the participant's legally acceptable representative's dated signature on a consent form along with the dated signature of the person conducting the consent discussion.

A copy of the signed and dated consent form should be given to the participant before participation in the trial.

The initial informed consent form, any subsequent revised written informed consent form and any written information provided to the participant must receive the IRB/ERC's approval/favorable opinion in advance of use. The participant or his/her legally acceptable representative should be informed in a timely manner if new information becomes available that may be relevant to the participant's willingness to continue participation in the trial. The communication of this information will be provided and documented via a revised consent form or addendum to the original consent form that captures the participant's dated signature or by the participant's legally acceptable representative's dated signature.

Specifics about a trial and the trial population will be added to the consent form template at the protocol level.

The informed consent will adhere to IRB/ERC requirements and applicable laws and regulations.

8.1.1.2 Inclusion/Exclusion Criteria

All inclusion and exclusion criteria will be reviewed by the investigator or qualified designee to ensure that the participant qualifies for the trial.

8.1.1.3 Medical History

A medical history will be obtained by the investigator or qualified designee. Medical history will include all active conditions, and any condition diagnosed within the prior 10 years that are considered to be clinically significant by the Investigator. Details regarding the disease for which the participant has enrolled in this study will be recorded separately and not listed as medical history.

8.1.1.4 Prior and Concomitant Medications Review

8.1.1.4.1 Prior Medications

The investigator or qualified designee will review prior medication use, including any protocol-specified washout requirement, and record prior medication taken by the participant within 28 days before starting the trial. Treatment for the disease for which the participant has enrolled in this study will be recorded separately and not listed as a prior medication.

8.1.1.4.2 Concomitant Medications

The investigator or qualified designee will record medication, if any, taken by the participant during the trial. All medications related to reportable SAEs and ECIs should be recorded as defined in [Section 8.2](#).

8.1.1.5 Disease Details and Treatments

8.1.1.5.1 Disease Details

The investigator or qualified designee will obtain prior and current details regarding disease status.

8.1.1.5.2 Prior Treatment Details

The investigator or qualified designee will review all prior cancer treatments including systemic treatments, radiation and surgeries.

8.1.1.5.3 Subsequent Anti-Cancer Therapy Status

The investigator or qualified designee will review all new anti-neoplastic therapy initiated after the last dose of trial treatment. If a participant initiates a new anti-cancer therapy within 30 days after the last dose of trial treatment, the safety follow-up visit must occur before the first dose of the new therapy. Once new anti-cancer therapy has been initiated the participant will move into survival follow-up.

